Implementation of the dart-throwing motion plane in hand therapy after distal radius fractures: preliminary results

Statistical Analysis Plan

Radiological measurements were performed considering radial height, radial inclination, volar tilt, intra-articular step-off and ulnar variance, both preoperatively and postoperatively. For each subject, the researchers calculated the residual deficit in all of the parameters between the evaluation post treatment and the evaluation at baseline (percentage = $100 - \text{post} / \text{pre} \cdot 100$). For the pinch and grip strength tests, measured post treatment, the researchers calculated the percentages of the values of the injured hand in relation to the uninjured hand (percentage = $\text{injured} / \text{uninjured} \cdot 100$).

Statistical analyses were performed in IBM SPSS software, v25 (IBM, Armonk, NY). The Shapiro-Wilk test of normality was used on all acquired variables. The majority of variables were not normally-distributed so a-parametric tests were applied. Descriptive statistics were used to describe the personal characteristics of the subjects in both groups (the received treatment, age, sex, injured hand, hand dominance and fracture pattern). The researchers used the Chi-Square test for categorical variables and the Mann-Whitney U test for numeric variables, when comparing parameters between groups. Significance was set at $p < 0.05$.

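### For numeric outcomes the SAP plans only a Mann-Whitney p-value read against 0.05 and calls for no effect estimate or confidence interval, so the size and uncertainty of the DTM effect go unquantified

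*SAP*

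**What the plan says.** The second paragraph of the SAP holds all of the between-group analysis. Two methods are named. For categorical variables, "The researchers used the Chi-Square test for categorical variables". For the rest, the plan is "the Mann-Whitney U test for numeric variables, when comparing parameters between groups". The decision rule is a single threshold: "Significance was set at" p < 0.05, with no statement of sidedness.

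Descriptive statistics are mentioned once: "Descriptive statistics were used to describe the personal characteristics of the subjects in both groups". The list that follows covers treatment received, age, sex, injured hand, dominance and fracture pattern. No outcome is on it.

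The first paragraph of the SAP defines two derived percentages. One is the residual deficit, 100 - post/pre × 100: "For each subject, the researchers calculated the residual deficit in all of the parameters". The other is for post-treatment pinch and grip strength, injured/uninjured × 100: "the researchers calculated the percentages of the values of the injured hand in relation to the uninjured hand".

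The title is "Implementation of the dart-throwing motion plane in hand therapy after distal radius fractures: preliminary results".

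**The concern.** A Mann-Whitney test, as planned, delivers a p-value. It does not by itself give a between-group difference on the outcome's own scale or an interval around one. The two percentage formulas do not fill the gap, because each produces a value for one subject and not a contrast between DTM and Sagittal.

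This matters more here than in a confirmatory trial. The chief use of a preliminary comparison is to show what effect sizes the data support and which they rule out, so that someone can decide whether DTM deserves further testing. A p-value against a threshold does not answer that. A non-significant result may come with an interval that excludes any worthwhile benefit, or with one that includes a large benefit, and the planned output does not separate the two. A significant result would likewise carry no size.

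The point does not depend on how many outcomes are tested or on baseline adjustment. One well-chosen outcome analysed under this plan would lack the same information.

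**Working it through.** **Is an estimate or interval called for anywhere?** The protocol and the SAP were read in full. Neither mentions a median or mean difference, a Hodges-Lehmann estimate, a probability of superiority, any other effect size, or a confidence interval. The outcomes that can be identified are range of motion, pain levels and functional tests (protocol, first paragraph) and the radiological measures, residual-deficit percentages and pinch and grip percentages (SAP, first paragraph). All are numeric or appear to be, although the pain and functional scales are not defined. No categorical outcome is named; Chi-Square as planned would also give only a p-value.

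**Is there a figure to reproduce?** No. The documents state no sample size, SD, target effect, power or allocation ratio. Everything below is an illustration. Its inputs are assumptions: equal arms of n, normal outcomes with a common SD, a pure location shift, and two-sided 0.05. Only the 0.05 comes from the SAP.

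**Same p-value, different evidence.** The large-sample standard error of the shift, in SD units, is

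SE = sqrt(2/n) / sqrt(3/π),

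where 3/π is the relative efficiency of the Mann-Whitney test under normality. A two-sided p = 0.20 corresponds to z = 1.28, so the estimate is 1.28 × SE and the 95% half-width is 1.96 × SE. At n = 10, SE = 0.447/0.977 = 0.458, the estimate is 0.59 and the half-width 0.90.

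| n per arm | 95% half-width (SD) | Estimate at p = 0.20 (SD) | 95% CI |
|---|---|---|---|
| 10 | 0.90 | 0.59 | -0.31 to 1.48 |
| 15 | 0.73 | 0.48 | -0.25 to 1.21 |
| 20 | 0.63 | 0.41 | -0.22 to 1.05 |
| 30 | 0.52 | 0.34 | -0.18 to 0.86 |
| 50 | 0.40 | 0.26 | -0.14 to 0.66 |

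The p-value is the same in every row, but the effects still compatible with the data differ widely.

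**What a non-significant result would leave open.** The planned test was simulated (4000 runs per setting), with the distribution-free Hodges-Lehmann interval computed alongside. Repeat runs differ by one or two percentage points.

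| n per arm | Power at true 0.5 SD | Mean half-width (SD) | Non-significant intervals containing +0.5 SD: true effect 0.5 SD | Same: true effect zero |
|---|---|---|---|---|
| 10 | about 16% | 0.98 | about 98% | about 85% |
| 15 | about 24% | 0.77 | about 97% | about 78% |
| 20 | about 33% | 0.66 | about 97% | about 69% |
| 30 | about 46% | 0.53 | about 95% | about 54% |

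The simulated half-widths slightly exceed the large-sample ones at small n, as expected. With 50 per arm and no true effect, the last column falls to about 33%.

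The last two columns bear on this point. The power column describes small samples, and adding an interval would not change it. It shows only how often the situation in the last two columns would arise.

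**The case against.** The case against has several parts, and some of it stands.

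- **Silence is not exclusion.** The SAP is two paragraphs long. It does not say that descriptive statistics are confined to personal characteristics, and it does not bar outcome summaries. A reader might infer that the trial will yield nothing but significant or not-significant labels. The text does not support that: group summaries may well be reported. They are not called for, however, and summaries alone would give no interval for the difference.
- **Mann-Whitney is not the only test.** A reader might also infer that it is the sole inferential method for every outcome. Chi-Square is listed too, and the documents do not state that all outcomes are numeric. The point is therefore limited to numeric outcomes.
- **The trial is not incapable of estimating the effect.** The recorded data would allow an estimate with an interval. It is the analysis as planned that does not ask for one.
- **Misreading is a prediction.** It is tempting to say that p ≥ 0.05 will be read as no difference. The SAP sets a threshold and contains no rule of interpretation, no equivalence claim and no adoption decision. The risk is real, but it is not written into the plan.
- **The numbers are not this trial's.** Sample size, SD and equal arms are assumed. Normality is assumed against the SAP's own statement that most variables failed it. Nothing in the documents marks 0.5 SD as a useful effect. This stands, and the figures are illustrative only.
- **The Hodges-Lehmann estimate is not assumption-free.** The Mann-Whitney test of identical distributions needs no shift model, but reading the Hodges-Lehmann value as the difference between groups does. On a ratio scale such as 100 - post/pre × 100, a common shift is doubtful. The ratio is undefined when the baseline is zero. Its sign also reverses between measures that should rise, such as range of motion, and measures that should fall, such as pain. This stands and shapes the fix.

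None of this supplies the missing estimate or interval.

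**Conclusion.** The point holds in a limited form. For numeric outcomes the SAP specifies a rank test and a threshold and stops there. It calls for no effect estimate and no interval, so the analysis as planned does not quantify the DTM effect or its uncertainty. This rests on the text alone and needs no assumption.

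How much that costs cannot be computed from the documents. If the trial has 10 to 30 per arm, equal arms and roughly normal outcomes, non-significant results would be weak evidence against a 0.5 SD benefit, as the last two columns of the simulation table show. The argument is strongest for small arms and weakens as they grow.

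The test itself is not invalid. This is a cheap improvement that should be made, because it changes what a preliminary trial can conclude. It does not affect the design or the data.

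**What to change.** Extend the analysis paragraph of the SAP along these lines:

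1. For each numeric outcome, report each group's median and interquartile range.
2. Report the Hodges-Lehmann estimate, defined as the median of all pairwise DTM minus Sagittal differences, with its 95% confidence interval.
3. State for each outcome which direction favours DTM. This is essential for the residual-deficit percentage, whose sign depends on whether improvement raises or lowers the measure.
4. State that reading the estimate as a common shift is an added assumption. Where a shift is implausible, give P(DTM > Sagittal) with a 95% confidence interval.
5. Keep the Mann-Whitney p-value as supportive. Word conclusions from the estimate and interval, and do not report p ≥ 0.05 as absence of a difference.

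The cost is a few sentences and an extra table column. No patients, visits or measurements are added. The SAP is written in the past tense, but the change can still be made by re-analysing recorded data. The downside is that wide intervals will make the results look less decisive.

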Implementation of the dart-throwing motion plane in hand therapy after distal radius fractures: preliminary results

Study Protocol

Each subject read and signed an informed consent form pretrial. Then, personal information, upper limb range of motion (ROM), pain levels and functional tests were recorded by a hand therapist. The Sagittal group activated the wrist mostly in the sagittal plane while the research group activated the wrist also in the dart throwing motion (DTM) plane, via the dart splint orthosis applied by a hand therapist.

All of the subjects in both groups received 12 therapy sessions, 30 minutes each one, 2-3 times a week, during 6-8 weeks following the removal of the cast. Certified hand therapists used conventional treatment techniques during the sessions. Both groups were instructed to exercise at home, 3 times a day, 10 minutes per exercise session. The dart splint orthosis was fitted to the subjects in the DTM group on their first evaluation session. They were instructed to use the dart splint orthosis at home. For each 10-minute exercise session, they were asked to perform 5 minutes of radial-extension under resistance and then 5 minutes ulnar-flexion under resistance. In addition, this group was required to fill in a chart at the end of each practice session, throughout the intervention period. The evaluator performed weekly phone calls to remind the DTM group to fill these out. The Sagittal group was instructed to perform at home active wrist motion similar to that practiced during the supervised therapy sessions. The prescribed instructions were similar to the exercises performed during the sessions. At the completion of the treatment, the subjects were reexamined by the same evaluator.

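### Received treatment is recorded but used in no between-group outcome comparison, so an imbalance in it could be read as a DTM effect if it also influences outcome

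*SAP*

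**What the plan says.** The SAP names the characteristics to be described in both groups: "the received treatment, age, sex, injured hand, hand dominance and fracture pattern". Received treatment comes first in that list and is not defined. Its role is descriptive.

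The between-group methods take up one sentence. "The researchers used the Chi-Square test for categorical variables", and numeric variables get "the Mann-Whitney U test for numeric variables, when comparing parameters between groups". The significance level is 0.05. The SAP gives no covariate-adjusted model, stratified test, subgroup or sensitivity analysis.

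Two other places bear on what received treatment means. The SAP has radiological measurements taken "both preoperatively and postoperatively", and the Protocol schedules therapy "during 6-8 weeks following the removal of the cast".

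Baseline enters in one way only. Most outcomes are expressed as "the residual deficit in all of the parameters between the evaluation post treatment and the evaluation at baseline", a percentage of the subject's own starting value. Pinch and grip are compared after treatment only, as the injured hand relative to the uninjured one.

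The Protocol describes a Sagittal group and a DTM group. Neither document says how subjects came to be in one or the other, or mentions stratification or matching.

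**The concern.** How a wrist fracture was managed could plausibly affect motion, pain, function and strength in the weeks after cast removal. If the two groups contain different mixes of management, an unadjusted rank test cannot separate that difference from the effect of the therapy. Nothing in the documents shows that the mix was balanced by design, and nothing in the analysis accounts for it.

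The residual-deficit formula may absorb part of a difference in starting level. It does not remove a difference in the rate of recovery between management types. Pinch and grip use no baseline value of the injured hand, so they lack even that partial protection.

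There is a smaller cost even with balanced groups. Variation between management types stays in the comparison as noise, in a study whose title calls its results preliminary.

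**Working it through.** **Plan's own figure.** There is none to reproduce. The documents state no sample size, power, effect size or SD.

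**Inputs from the SAP.** Two-group Mann-Whitney U test at 0.05 (two-sidedness is assumed), with received treatment in no comparison.

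**Assumptions, not from the documents.** Received treatment has two levels. It shifts a normally distributed outcome by 0.2 to 1.0 within-level SD. There are 20 subjects per group (10 and 30 also tried). There is no true DTM effect.

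**Step 1: bias.** Bias in the group difference = imbalance x shift.
- 20 points: 0.20 x 0.5 = 0.10 SD to 0.20 x 1.0 = 0.20 SD
- 30 points: 0.30 x 0.5 = 0.15 SD to 0.30 x 1.0 = 0.30 SD
- 40 points: 0.40 x 0.5 = 0.20 SD to 0.40 x 1.0 = 0.40 SD
- Shift of 0: no bias at any imbalance

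**Step 2: false-positive rate given a fixed imbalance.** Simulation, 20 per group, 20,000 runs per setting:

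| Imbalance | Shift 0.5 SD | 0.8 SD | 1.0 SD |
|---|---|---|---|
| 20 points | 5.4% | 5.7% | 6.3% |
| 30 points | 6.5% | 8.6% | 10.9% |
| 40 points | 8.1% | 13.3% | 17.0% |

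The van Elteren test, stratified by received treatment, stayed at 4.7-5.4% throughout. At a 30-point imbalance a 0.2 SD shift gives 4.9% and a 0.3 SD shift 5.4%, so weak prognostic effects do no visible harm.

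Group size matters. In a separate run of 4,000 replicates at 40 points, shifts of 0.5 and 1.0 SD gave 6.0% and 10.4% with 10 per group, and 10.8% and 25.4% with 30 per group. At 20 points the highest rate was 7.8% (30 per group, 1.0 SD).

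**Step 3: if allocation was simple randomisation.** With half of subjects at each level, the counts in the two groups are independent Binomial(20, 0.5). The probability of an imbalance of at least 20 points is 27%, of at least 30 points 8.1%, and of at least 40 points 1.7%. Averaged over such allocations, the unadjusted test rejects in 4.8% (0.5 SD) and 5.1% (1.0 SD) of runs, so overall type I error holds.

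**Step 4: power with balanced groups.** With a true effect of 0.8 SD and 20 per group, unadjusted power is 64%, 60% and 57% for shifts of 0.5, 0.8 and 1.0 SD. The stratified test gives 65-66%. The largest loss is 66 - 57 = 9 points.

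**The case against.** The case against has real force on several counts.

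- **Mixed management is inferred.** A reader might conclude that the sample certainly combined operated and unoperated subjects. The documents do not establish this. Radiology before and after surgery is stated without exception, and a cast can follow an operation. Only the listing of received treatment as a characteristic to be described suggests that it varied.
- **Imbalance alone does not bias the comparison.** A reader might infer that any difference in received treatment feeds directly into the DTM effect. It does so only as far as the factor influences outcome, and the documents give no figure for that or for the actual imbalance. The SAP also names tests rather than an effect estimate.
- **The inflated rates are conditional.** A reader might take 7-17% as this trial's error rate. It applies only if a large imbalance occurred. Under randomisation the larger imbalances are uncommon and overall error is held. The documents neither state nor exclude randomisation, so this defence is possible but cannot be confirmed from the text.
- **The choice of factor is open to debate.** Fracture pattern and age are in the same list, and nothing ranks received treatment above them. An unadjusted rank test is an accepted simple choice for preliminary work, and a descriptive table would make an imbalance visible.
- **Pre-specification is no longer possible.** The SAP reports, in the past tense, that most variables failed the normality check, so it was written after the data were examined.

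These points limit the claim and shape the remedy. They do not remove the gap: a described imbalance would still be uncorrected, and no design feature in the documents makes correction unnecessary.

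**Conclusion.** The point holds in a conditional form. Received treatment is collected, no outcome comparison uses it, and no allocation method is given that would balance it. If it affects outcome by 0.5 to 1.0 SD and differs by 30 to 40 points between groups of 20, the Mann-Whitney false-positive rate is roughly 7-17% in place of 5%. With a 20-point difference or a shift of 0.2 SD or less, the rate stays near 5%. If allocation was random, the issue reduces to chance imbalance and up to about 9 points of power.

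Group size, number of levels, imbalance and prognostic shift are all assumed. The direction and size of any actual bias cannot be known from the documents. The change is worth making because it is cheap and the data are already held, not because bias has been shown.

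**What to change.** 1. Define received treatment and its levels, and report its distribution in each group.
2. State how the groups were formed.
3. For each numeric outcome, report a van Elteren test stratified by received treatment beside the unadjusted Mann-Whitney result. This is the direct stratified extension of the planned test and needs no normality assumption.
4. If a model is preferred, use ANCOVA on the raw post-treatment value, with received treatment and, where it was measured, the baseline value as covariates. The residual-deficit percentage should not be the response there, since it already contains baseline.
5. Label the adjusted analysis as post hoc, and do not choose the factor from baseline p-values.

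The cost is some SAP wording and a short additional analysis of existing data. A model spends one degree of freedom for each treatment level beyond the first, and stratification loses some information where strata are small.
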